7.4. Subject Withdrawal Criteria

7.4.1. Subject Stopping Rules

Subjects in Cohorts 2A, 2B, 3A, and 3B will be followed through Outpatient Visit 4 (OV4) of the first dosing period, and will not receive the second single dose:

- If the subject develops anaphylaxis or a related Grade 3 or Grade 4 AE
- If the subject has a persistent (i.e., >5 days with no response to treatment) Grade ≥ 2 rash considered related to the investigational drug by the Principal Investigator ([Appendix 4](#))
- If the Investigator believes that it is in the best interest of the subject to not receive a second dose
- If the subject no longer meets all eligibility criteria prior to the second single dose
- If the subject becomes pregnant prior to the second single dose

If a subject is removed from the study for any reason, the subject will be followed for resolution of any ongoing AE(s).

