11.3. Adverse Event Reporting

11.3.1. Notification of Serious Adverse Events

The Sponsor has requirements for expedited reporting of SAEs meeting specific criteria to worldwide regulatory authorities in accordance with ICH guidelines and local regulatory requirements. Therefore, the Investigator must notify the Sponsor immediately regarding any SAE that occurs after informed consent via transmission of a Serious Adverse Event Report (SAER) by the study site to the safety vendor by email within 24 hours of awareness that an SAE has occurred, with a copy to the Medical Monitor. Contact details will be provided to the site(s). An optional initial report can be made via telephone, but a completed SAER must still be emailed within 24 hours of the site's knowledge of the event.

The Investigational site will be provided with SAER forms wherein the following information is requested:

- Subject identification, Investigator name, and site number
- SAE information: event term, onset date, severity, and causal relationship
- The outcomes attributable to the event (e.g., death, a life-threatening AE, inpatient hospitalization, prolongation of existing hospitalization, a persistent or significant disability or incapacity, or other important medical event[s]; refer to [Section 11.4.4](#))
- A summary of relevant test results, pertinent laboratory data, and any other relevant medical history
- The date of study drug administration (NOTE: as this is a double-blind study, SAERs should not indicate specific study drug assignments)
- Indicate if the study drug was discontinued (i.e., if the second single dose is not administered to subjects in Cohorts 2A, 2B, 3A, or 3B)

Supplemental information may be requested, including the following: hospital records, laboratory results, radiology reports, progress notes, admission and emergency room notes, holding and observation notes, discharge summaries, autopsy reports, and death certificates.

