4 ANALYSIS POPULATIONS

The following populations will be defined:

- **Enrolled Population:** All subjects who provide informed consent and are randomized.
- **Safety Population:** The safety population will include all randomized subjects who receive any amount of study drug.
- **Pharmacokinetic Population:** The PK population will include all randomized subjects who have received at least a portion of 1 dose of CD388 and have at least 1 evaluable postdose concentration value. Subjects administered matching placebo will not be included in the PK population.

Pharmacokinetic Completer Population: [Dose Groups 2A, 2B, 3A, and 3B only] The PK population will include all randomized subjects who have received 2 single doses of CD388 and obtained PK samples at all visits.

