8 SAFETY ANALYSIS

Unless otherwise specified, all available data will be listed and summary tables for safety assessments will be presented by injection route (IM or SQ), CD388 dose, and pooled placebo for the safety population as detailed in [Table 6](#).

Continuous variables will be summarized (absolute values and change from baseline) using descriptive statistics. The TEAEs occurring after the first single dose and after the second single dose will be analyzed separately.

Table 6: Data Presentations for Safety Assessment

Data	Variables	Presentation
Adverse events	Adverse event, description, date and time, severity, relationship to study drug, action taken with study drug, whether the AE caused the subject to discontinue from the study, study days, and outcome, Duration of AE, Date and time of onset, date, and time of resolution.	
Listings:
 
• Reported AEs,• Serious Adverse Event (SAE) 
Summary Tables, including number and percentage of subjects experiencing:
 
• Treatment-emergent adverse events (TEAEs),• TEAEs related to study drug• TEAEs by severity,• Serious TEAEs,• Influenza-like TEAEs (reported during the outpatient follow-up period),• Adverse Events of Special Interest (AESIs),• TEAEs leading to study withdrawal• TEAEs leading to study drug withdrawal (cohorts 2a, 2b, 3a, 3b)• Overall summary will include:
○ At Least One TEAE○ At Least One Drug-Related TEAE○ Maximum Severity:
➢ Mild,➢ Moderate➢ Severe➢ Life-threatening➢ Death○ At Least One SAE○ At Least One Drug-Related SAE○ Death○ AE leading to study drug withdrawal (Pooling placebo from cohorts 2a, 2b, 3a, 3b)○ AE leading to study withdrawal
Concomitant medications	All medications taken during the study (as defined in the protocol and including prior medications that are continued), dose, units, route, indication/ reason taken, and date and time.	
Listing
 
• Note: includes coded terms (anatomic therapeutic chemical [ATC] level 4 and preferred name)

Data	Variables	Presentation																
Extent of exposure	Study drug administration dose, Route, units, date, time, Cohort	
Listing
																

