	CD388 50 mg (N = XX)	CD388 150 mg (N = XX)	CD388 450 mg (N = XX)	Pooled Placebo (N = XX)	CD388 50 mg (N = XX)	CD388 150 mg (N = XX)	CD388 450 mg (N = XX)	CD388 900 mg (N = XX)	Pooled Placebo (N = XX)	
	n (%)	n (%)	n (%)	n (%)	n (%)	n (%)	n (%)	n (%)	n (%)	
Subjects With at Least One TEAE [1][2]	xx (xx.x)	xx (xx.x)	xx (xx.x)	xx (xx.x)	xx (xx.x)	xx (xx.x)	xx (xx.x)	xx (xx.x)	xx (xx.x)	
Subjects With At Least One Drug-Related TEAE [2] [3]	xx (xx.x)	xx (xx.x)	xx (xx.x)	xx (xx.x)	xx (xx.x)	xx (xx.x)	xx (xx.x)	xx (xx.x)	xx (xx.x)	
Maximum Severity [2]										
Mild	xx (xx.x)	xx (xx.x)	xx (xx.x)	xx (xx.x)	xx (xx.x)	xx (xx.x)	xx (xx.x)	xx (xx.x)	xx (xx.x)	
Moderate	xx (xx.x)	xx (xx.x)	xx (xx.x)	xx (xx.x)	xx (xx.x)	xx (xx.x)	xx (xx.x)	xx (xx.x)	xx (xx.x)	
Severe	xx (xx.x)	xx (xx.x)	xx (xx.x)	xx (xx.x)	xx (xx.x)	xx (xx.x)	xx (xx.x)	xx (xx.x)	xx (xx.x)	
Life-threatening	xx (xx.x)	xx (xx.x)	xx (xx.x)	xx (xx.x)	xx (xx.x)	xx (xx.x)	xx (xx.x)	xx (xx.x)	xx (xx.x)	
Death	xx (xx.x)	xx (xx.x)	xx (xx.x)	xx (xx.x)	xx (xx.x)	xx (xx.x)	xx (xx.x)	xx (xx.x)	xx (xx.x)	
Subjects With at Least One TEAE SAE [2]	xx (xx.x)	xx (xx.x)	xx (xx.x)	xx (xx.x)	xx (xx.x)	xx (xx.x)	xx (xx.x)	xx (xx.x)	xx (xx.x)	
Subject with at Least One TEAE Drug-Related SAE [2] [3]	xx (xx.x)	xx (xx.x)	xx (xx.x)	xx (xx.x)	xx (xx.x)	xx (xx.x)	xx (xx.x)	xx (xx.x)	xx (xx.x)	
Death [2]	xx (xx.x)	xx (xx.x)	xx (xx.x)	xx (xx.x)	xx (xx.x)	xx (xx.x)	xx (xx.x)	xx (xx.x)	xx (xx.x)	
Leading to study withdrawal [2]	xx (xx.x)	xx (xx.x)	xx (xx.x)	xx (xx.x)	xx (xx.x)	xx (xx.x)	xx (xx.x)	xx (xx.x)	xx (xx.x)	

Date: VERSION - YYYY-MM-DD

Data Source: XXXX

Program Source: XXXXX.sas

IM = Intramuscular; SQ = Subcutaneous; TEAE = Treatment-Emergent Adverse Event.

Notes:

[1] A Treatment-Emergent Adverse Event (TEAE) is an adverse event which starts or worsens after treatment with study drug.

[2] Percentages are based on the number of subjects in the Safety population (N).

[3] Drug-related TEAEs are those TEAEs reported by the Investigator as having a "Reasonable Possibility" of being related to study treatment.

<Programming Note>

Table 14.3.1.2: "Treatment-Emergent Adverse Events (TEAEs) - Second Dose - Overall Summary" i.e., Cohorts 2A, 2B, 3A, 3B, and pooled placebo of respective route will follow the same layout.

Table 14.2.14 Template T3.2: Treatment-Emergent Adverse Events (TEAEs) by System Organ Class and Preferred Term (Safety Population)

Table 14.3.1.3

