Table 14.3.1.10: "Serious Treatment-Emergent Adverse Events (TEAEs) by System Organ Class and Preferred Term - Second Dose" i.e., Cohorts 2A, 2B, 3A, 3B, and pooled placebo of respective route will follow the same layout.

Table 14.2.18 Template T3.6: Influenza-like Treatment-Emergent Adverse Events (TEAEs) by System Organ Class and Preferred Term (Safety Population)

Table 14.3.1.13
 Influenza-like Treatment-Emergent Adverse Events (TEAEs) by System Organ Class and Preferred Term - First Dose
 (Safety Population)

MedDRA System Organ Class Preferred Term	IM Route				SQ Route				Pooled Placebo (N = XX)
	CD388 50 mg (N = XX)	CD388 150 mg (N = XX)	CD388 450 mg (N = XX)	Pooled Placebo (N = XX)	CD388 50 mg (N = XX)	CD388 150 mg (N = XX)	CD388 450 mg (N = XX)	CD388 900 mg (N = XX)	
	n (%)	n (%)	n (%)	n (%)	n (%)	n (%)	n (%)	n (%)	
Subjects with at least one TEAE	xx (xx.x)	xx (xx.x)	xx (xx.x)	xx (xx.x)	xx (xx.x)	xx (xx.x)	xx (xx.x)	xx (xx.x)	xx (xx.x)
SOC 1	xx (xx.x)	xx (xx.x)	xx (xx.x)	xx (xx.x)	xx (xx.x)	xx (xx.x)	xx (xx.x)	xx (xx.x)	xx (xx.x)
PT 1	xx (xx.x)	xx (xx.x)	xx (xx.x)	xx (xx.x)	xx (xx.x)	xx (xx.x)	xx (xx.x)	xx (xx.x)	xx (xx.x)
PT 2	xx (xx.x)	xx (xx.x)	xx (xx.x)	xx (xx.x)	xx (xx.x)	xx (xx.x)	xx (xx.x)	xx (xx.x)	xx (xx.x)
PT 3	xx (xx.x)	xx (xx.x)	xx (xx.x)	xx (xx.x)	xx (xx.x)	xx (xx.x)	xx (xx.x)	xx (xx.x)	xx (xx.x)
SOC 2	xx (xx.x)	xx (xx.x)	xx (xx.x)	xx (xx.x)	xx (xx.x)	xx (xx.x)	xx (xx.x)	xx (xx.x)	xx (xx.x)
PT 1	xx (xx.x)	xx (xx.x)	xx (xx.x)	xx (xx.x)	xx (xx.x)	xx (xx.x)	xx (xx.x)	xx (xx.x)	xx (xx.x)
PT 2	xx (xx.x)	xx (xx.x)	xx (xx.x)	xx (xx.x)	xx (xx.x)	xx (xx.x)	xx (xx.x)	xx (xx.x)	xx (xx.x)
PT 3	xx (xx.x)	xx (xx.x)	xx (xx.x)	xx (xx.x)	xx (xx.x)	xx (xx.x)	xx (xx.x)	xx (xx.x)	xx (xx.x)
...	xx (xx.x)	xx (xx.x)	xx (xx.x)	xx (xx.x)	xx (xx.x)	xx (xx.x)	xx (xx.x)	xx (xx.x)	xx (xx.x)

Date: VERSION - YYYY-MM-DD

Data Source: XXXX

Program Source: XXXXX.sas

IM = Intramuscular; SQ = Subcutaneous.

Notes:

For each row category, a subject with two or more adverse events in that category is counted only once.

Percentages are based on the number of subjects in the safety population (N).

Influenza-like TEAE are those events which were collected during Follow-up Period.

Adverse events are coded into system organ class and preferred term using MedDRA Version 24.1.

<Programming Note>

Table 14.3.1.14: "Influenza-like Treatment-Emergent Adverse Events (TEAEs) by System Organ Class and Preferred Term - Second Dose"

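### The second-dose adverse event percentages are taken over the Safety population, which keeps subjects who never received the second dose; separately, the anti-drug antibody table has placebo columns although placebo samples are not assayed

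*SAP*

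**What the plan says.** **Population.** SAP section 4 defines one safety set: "The safety population will include all randomized subjects who receive any amount of study drug". Protocol section 12.1 defines it the same way. SAP section 8 makes it the default: unless otherwise specified, "summary tables for safety assessments will be presented by injection route (IM or SQ), CD388 dose, and pooled placebo for the safety population".

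**Denominator.** The TEAE shells (Templates T3.1 to T3.6) all carry the same footnote: "Percentages are based on the number of subjects in the safety population (N)".

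**Second-dose tables.** Tables 14.3.1.2, .4, .6, .8, .10, .12 and .14 exist only as programming notes under those templates. The note for Table 14.3.1.2 reads "i.e., Cohorts 2A, 2B, 3A, 3B, and pooled placebo of respective route will follow the same layout". The notes restrict the cohorts but change neither the population nor the denominator.

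**Missed second doses are foreseen.** Protocol section 7.4.1 lists reasons why Cohort 2 and 3 subjects are followed through the last outpatient visit of the first period "and will not receive the second single dose". SAP section 3.1 provides for sentinel dropouts before the second dose.

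**A two-dose set exists, but only for PK.** For the PK Completer Population, SAP section 4 says: "The PK population will include all randomized subjects who have received 2 single doses of CD388 and obtained PK samples at all visits".

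**ADA.** Shell Table 14.2.5.1 has a pooled-placebo n (%) column for each route, with percentages over the Safety population. The Protocol Synopsis and section 6.1 say that samples are taken from everyone to protect the blind, but only those from the CD388 group are analysed.

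**The concern.** Safety after the repeated dose is a secondary endpoint. No hypothesis is tested, so the printed percentages are the result. A subject who never received the second dose is not at risk of a second-dose event. Counting that subject in N can only lower the percentage.

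The dilution need not be equal across columns. Some of the section 7.4.1 reasons are tied to drug effect, such as a related Grade 3 or 4 event or a persistent related rash. Others, such as loss of eligibility, could occur in either group. If re-dosing differs between columns, the CD388-to-placebo comparison shifts as well as the level.

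The omission looks like an oversight. The SAP analyses second-dose TEAEs separately, allows study day to be counted from the second dose (section 10.1), defines a second-dose baseline (section 10.3) and has a two-dose set for PK. It did not carry this through to the safety denominator.

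In the ADA table, a placebo percentage invites the reader to see a tested comparison group where nothing was tested.

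**Working it through.** **Planned counts.** Protocol Table 5 and SAP Table 2 give each cohort 1 + 7 = 8 CD388 and 1 + 2 = 3 placebo subjects. Seven cohorts give 7 × 8 = 56 CD388 and 7 × 3 = 21 placebo, total 77, which matches the stated figure. For the second dose, each CD388 column (one cohort) has 8 planned subjects. Placebo pooled over two cohorts per route has 2 × 3 = 6.

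**Formula.** Let x be the number of re-dosed subjects with a second-dose TEAE, N the column's Safety count, and k the number not re-dosed.

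printed rate = x/N = [x/(N − k)] × (N − k)/N = true rate × (N − k)/N

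The documents do not give k, so a range is shown.

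**CD388 column, N = 8, no replacement, example x = 2:**

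| k | Factor (8 − k)/8 | Printed | Among re-dosed | Shortfall (points) |
|---|---|---|---|---|
| 0 | 1.000 | 25.0% | 25.0% | 0 |
| 1 | 0.875 | 25.0% | 2/7 = 28.6% | 3.6 |
| 2 | 0.750 | 25.0% | 2/6 = 33.3% | 8.3 |
| 3 | 0.625 | 25.0% | 2/5 = 40.0% | 15.0 |

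**Placebo per route, N = 6:** the factor is 5/6 = 0.833 for k = 1 and 4/6 = 0.667 for k = 2.

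**CD388-to-placebo ratio.** The printed ratio is the true ratio times [(8 − k₁)/8] / [(6 − k₂)/6], where k₁ is the CD388 and k₂ the placebo number not re-dosed.
- k₁ = 1, k₂ = 0: 0.875.
- k₁ = 0, k₂ = 1: 1/0.833 = 1.20.

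**How likely is k > 0?** No dropout rate is stated. Assume independent chances of 5%, 10% or 20% of missing the second dose. The probability that at least one of 8 subjects in a column misses it, 1 − (1 − p)⁸, is then 34%, 57% or 83%. For at least one of the 4 × 8 = 32 CD388 subjects in Cohorts 2 and 3 it is 81%, 97% or above 99%. These rates are illustrations, not document figures.

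**ADA.** Planned placebo subjects are 9 (IM) + 12 (SQ) = 21. The number assayed by design is 0, so no placebo percentage exists to report.

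**The case against.** **Shells may change.** The introduction to the table shells lists footnotes among the details that may differ in the final tables, and SAP section 12 allows slight changes of format and layout. A programmer might therefore print the re-dosed N. This weakens any claim that the final tables will certainly be wrong. It does not supply the missing rule: section 8 still assigns the Safety population, and no passage gives a re-dosed denominator.

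**The effect is conditional and recoverable.** It is zero if everyone is re-dosed. The analyses are descriptive, n is printed beside each percentage, and Listing 16.2.5.2 (second-dose administration) gives the re-dosed count. Protocol section 7.5 also allows replacement of subjects withdrawn for reasons other than adverse events, so N may exceed 8. One replaced dropout would give 8/9 = 0.889 rather than 0.875. All of this stands and limits the weight of the point.

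**Evidence of missed doses.** Protocol section 11.3.1 mentions a field to complete "if the second single dose is not administered to subjects in Cohorts 2A, 2B, 3A, or 3B", but that is an item on the serious adverse event form, not a general record of missed doses. The case rests on Protocol 7.4.1 and SAP 3.1.

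**Wider readings that the documents do not support.**
- A reader might infer the same error in the tables of potentially clinically significant (PCS) values. The laboratory shell (Template T4.2) covers any post-baseline visit and is not a second-dose table. In a second-dose version, a subject not re-dosed would have no predose baseline under SAP 10.3 and so could not enter the denominator. Requiring that baseline is not a usable remedy for laboratory data: the second-dose schedule places laboratory tests on Day -1 and Day 2, not Day 1.
- The reactogenicity shell (Table 14.3.5.1) is not split by dose, so it contains no second-dose percentage to correct.
- One might read the second-dose placebo pool as whole-route placebo (9 IM, 12 SQ), giving factors of 6/9 = 0.67 and 6/12 = 0.50. The note opens by naming Cohorts 2A to 3B, so pooling within those cohorts is the more natural reading. The note should simply say so.
- That untested placebo subjects would print as 0 (0.0%) in the ADA table is an inference. The cells are placeholders, the ADA listing has a column for tests not done, and SAP section 9 leaves the ADA analysis open. The mismatch between the placebo columns and the assay plan remains.

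**Conclusion.** The point holds for the seven second-dose TEAE tables. Followed as written, the plan prints second-dose rates too low in any column with a subject not re-dosed. The factor is (8 − k)/8 for a CD388 column, on the planned 8 subjects with no replacement. That is 0.875 to 0.625 for one to three subjects missed, and no error if none is missed.

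The consequence is small: a descriptive secondary endpoint, recoverable from a listing, with the primary single-dose endpoint untouched. It is still worth correcting, because the columns are small enough for one subject to move a percentage visibly.

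The ADA table is a separate and lesser mismatch, in an exploratory endpoint. The conclusion does not extend to the PCS or reactogenicity tables.

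**What to change.** 1. In SAP section 4, add a Second-Dose Safety Population: subjects who received any amount of the second dose.
2. Use it as N in Tables 14.3.1.2, .4, .6, .8, .10, .12 and .14, and correct the footnotes for those tables.
3. State in the programming notes that second-dose placebo is pooled from Cohorts 2A and 3A (IM) and from 2B and 3B (SQ).
4. In Table 14.2.5.1, base the percentage on CD388 subjects with an evaluable ADA result, and drop the placebo columns or mark them not assayed.

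The cost is one population definition and edits to footnotes and programming notes. No new data are needed.

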- k. At indicated visits, inspection of administration site and surrounding area will be performed twice daily (once between approximately 2–4 hours postdose, and once approximately 8–12 hours postdose), with any abnormal findings reported as AE s. Reactions will be rated according to the scale provided in [Table 7](#).
- l. For Cohorts 1A, 1B, 2A, 2B, 3B: Blood samples for PK analysis will be collected predose (-24 hour window); post-dose at 2, 4, and 12 hours (each \pm 10 minute window); 24 hours (\pm 30 minute window); 48 hours (\pm 1 hour window); 72, 96, 120 hours (each \pm 2 hour window); and Days 7, 9, 11, 14, 21, 30 (each \pm 2 hour window). Postdose samples collected at outpatient CRU visits at OV1, OV2, OV3, and OV4 have the same windows (i.e., in \pm days) as the visits.
For Cohort 3A: Blood samples for PK analysis will be collected predose (-24 hour window); post-dose at 12 and 24 hours (\pm 30 minute window); 48 hours (\pm 1 hour window); 72, 84, 96, 108, 120 hours (each \pm 2 hour window); and Days 7, 9, 11, 14, 21, 30 (each \pm 2 hour window). Postdose samples collected at outpatient CRU visits at OV1, OV2, OV3, and OV4 have the same windows as the visits.
- m. Blood samples for metabolite identification (e.g., free zanamivir, zanamivir dimers) and CD388 DAR distribution will be collected on Day 1 at 2 hours postdose, on Day 2 at 24 hours postdose, on Days 14 and 30, and at OV3. Urine samples for metabolite identification will be collected on Day 1 from 0–12 hours and from 12–24 hours postdose, on Day 2 from 24–48 hours postdose, on Day 14 over a 24-hour period, and over a 24-hour period that starts on Day 29 and ends prior to CRU check-out on Day 30.
- n. Serum samples for CD388 glycoforms will be collected predose on Day 1 and once in the morning on Days 2, 7, 14, 21, and 30, and at the OV1 and OV3 visits.
- o. A mandatory pharmacogenomic (DNA) blood sample will be collected once, preferably on Day 1 (collection at another time point is allowed if necessary) to allow for pharmacogenomic research related to CD388.
- p. Nasopharyngeal swab samples will be collected predose on Day 1, and on Days 2, 5, 7, 9, 11, 14, 21, and 30.
- q. Adverse events (including influenza-like illness which will be tested for both COVID-19 and flu) will be collected for all subjects from the time of signing the ICF through 4 months after the last dose of study drug, whichever is longer.

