- a. At each visit indicated in the Schedule of Events (Tables 1, 2, and 3).
- b. Performed at screening, and as clinically indicated (e.g., if the Investigator has concerns regarding an SAE, anti-drug antibody reaction in a subject with hypersensitivity reaction, fever, serious rash, joint/bone pain, cough, proteinuria, or clinically meaningful changes in the white cell differential or liver function tests).
- c. At screening only.
- d. If a subject develops signs and symptoms of an acute respiratory tract infection at any time during the study, COVID-19, influenza, and/or respiratory syncytial virus (RSV), nasopharyngeal rapid antigen test plus PCR will be performed.
- e. As indicated.
- f. At screening and Day -1, and during the outpatient visits if vital signs are abnormal.

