
 To determine the PK profile of CD388 Injection in upper respiratory tract after IM or SQ administration as a single dose to healthy adult subjects. 	
 Pharmacokinetic parameters following CD388 Injection administration: maximum nasopharyngeal (NP) concentration (C_{max}), time to maximum NP concentration (T_{max}), area under the NP concentration-time curve from time 0 to time of last quantifiable sample (AUC_{0-t}). 	Refer to Section 7

 To identify CD388 metabolites in plasma, CD388 and its metabolites in urine, and CD388 drug-antibody ratio (DAR) distribution in plasma, and CD388 glycoforms in serum after IM or SQ administration to healthy adult subjects. 	
 CD388 metabolites (e.g., free zanamivir, zanamivir dimers) in plasma and urine, CD388 in urine and nasal wash, CD388 DAR distribution in plasma, and CD388 glycoforms in serum, to be reported separately. 	Refer to Section 7

 To evaluate biomarkers that may be associated with AEs after CD388 Injection. 	
 Results of the analyses of exploratory biomarkers (including but not limited to cytokines, chemokines, acute phase reactants, etc.). 	Refer to Section 9

 To evaluate CD388 immunogenicity. 	
 Anti-drug antibody titers in blood (plasma or serum). 	Refer to Section 9

 To explore pharmacogenomics related to CD388. 	
 Results of the analyses of pharmacogenomic samples, to be reported separately. 	Refer to Section 9

Objective	Endpoint	Analysis

 • To explore the effects on cardiac safety in subjects administered CD388 Injection. 	
 • 12-lead ECG and Holter monitoring parameters. 	Refer to Section 8

 • To explore the effect of CD388 injection on the occurrence of influenza-like illness (during flu season). 	
 • Influenza-like illness reporting during the outpatient follow-up period. 	Refer to Section 8

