8.1 Adverse Events

Treatment-emergent adverse events (TEAEs) are AEs that are not present prior to the exposure to study drug or AEs that are already present that worsen in severity or frequency following exposure to study drug. All summary tables (except where noted) will present TEAEs. If a subject has more than one TEAE with the same PT (after the same dose, if applicable), it is counted once in the summary tables at the strongest relationship to study drug and at the highest severity.

All TEAEs will be coded using Medical Dictionary for Regulatory Activities (MedDRA) Version 24.1. The listing and summaries will include coded SOC and PT. Events will be listed by study drug, subject, and AE onset date. Treatment-emergent Adverse Event duration (stop date/time - start date/time), management, concomitant laboratory, vitals, and clinical examination abnormalities will be included in the listing.

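### The footnote to the influenza-like TEAE tables selects events by collection period alone, in conflict with the table title and SAP Table 6

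*SAP*

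**What the plan says.** The exploratory objective in SAP Section 2, Table 1 concerns the effect of CD388 "on the occurrence of influenza-like illness (during flu season"), and its endpoint is "Influenza-like illness reporting during the outpatient follow-up period". SAP Section 8, Table 6 lists the matching summary as "Influenza-like TEAEs (reported during the outpatient follow-up period").

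The shell for that summary is Template T3.6. Its first-dose table is titled "Influenza-like Treatment-Emergent Adverse Events (TEAEs) by System Organ Class and Preferred Term - First Dose", and the second-dose table, 14.3.1.14, uses the same layout. The footnote reads "Influenza-like TEAE are those events which were collected during Follow-up Period".

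The protocol treats influenza-like illness as one kind of adverse event. Note q to Protocol Table 1 refers to "Adverse events (including influenza-like illness which will be tested for both COVID-19 and flu").

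**The concern.** The footnote is the only written rule for choosing which events enter these two tables, and it is a rule about timing. A sprain or a headache recorded at an outpatient visit satisfies it as well as a febrile respiratory illness does. A programmer following it literally would produce a table of all follow-up TEAEs under an influenza-like heading. A programmer who applied a narrower filter would be using one that nobody has written down and that could be chosen after treatment codes are known. Either way, the one summary dedicated to this objective would not rest on a pre-specified event definition.

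**Working it through.** The plan states no figure on this point, so there is none to reproduce. The check is mainly textual.

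**1. Conditions imposed in each place**

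| Place | Influenza-like? | Period? |
|---|---|---|
| SAP Table 1, endpoint | yes | outpatient follow-up |
| SAP Table 6 | yes | outpatient follow-up |
| T3.6 title | yes | after first (or second) dose |
| T3.6 footnote | no | a follow-up period, not defined |

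The first two rows make timing a second condition on an influenza-like event. The footnote makes timing the whole condition.

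**2. Does the footnote act as a definition?** In Templates T3.1 and T3.3, drug-related TEAEs are defined by a note of the same grammatical form, and there the note states the selection rule. The natural reading is that the T3.6 note does so too.

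**3. Is the missing criterion supplied elsewhere?**
- SAP Section 8.1 defines TEAEs as "AEs that are not present prior to the exposure to study drug", or as existing events that worsen. It has no influenza-like element.
- The serology note to Protocol Table 6 (Section 9.5) begins "If a subject develops signs and symptoms of an acute respiratory tract infection at any time during the study" and then calls for respiratory virus testing. That triggers a test. It is not a case definition, and no table refers to it.
- The adverse event listing shell (Listing 16.2.7.1) has no influenza-like flag.
- No preferred-term list or symptom criterion appears in the protocol, the SAP or the shells.

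**4. Which rows are affected?** Influenza-like follow-up TEAEs are a subset of all follow-up TEAEs. The count under the footnote is therefore at least the intended count. The two are equal only if every subject with a follow-up TEAE also has an influenza-like one. The effect falls on the at-least-one-TEAE row and on the SOC rows. Individual preferred-term rows would still be correct for their own terms, although unrelated terms would be listed beside them.

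**5. How much does one subject move a row?** With the planned numbers in SAP Table 2:
- CD388 cohort: 1/8 = 12.5 percentage points
- pooled IM placebo: 1/9 = 11.1 percentage points
- pooled SQ placebo: 1/12 = 8.3 percentage points

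**6. What did the authors intend?** A programming note says the second-dose table will be omitted if there are no data. The other second-dose TEAE tables carry no such note. Up to 4 × 11 = 44 subjects are in the second-dose cohorts. Suppose each independently had a 10% to 30% chance of any follow-up TEAE (an assumption; the documents give no rate). The chance of an empty table under the literal rule would then run from 0.9^44 ≈ 0.010 down to 0.7^44 ≈ 1.5 × 10⁻⁷. Allowing for an empty table fits an uncommon subset better than all follow-up TEAEs.

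**The case against.** The best reply is that the footnote should be read with its title and with Table 6. On that reading it only adds the period limit to events already known to be influenza-like, and the note about an empty second-dose table supports this. That stands as evidence of intent, and a deliberate plan to tabulate everything should not be inferred. It does not rescue the footnote, because the influenza-like condition is still not written in any form a programmer could apply.

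The shells also allow footnotes to change in the final tables, and the endpoint is exploratory in a study with no formal hypothesis testing. Both points are fair and limit the importance of the matter.

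Four stronger readings are tempting, and the documents do not support them.
- *The table could not address the objective at all.* It is laid out by SOC and preferred term, so relevant terms could still be found by arm.
- *Counting COVID-19 is an error.* The endpoint is a syndrome, not laboratory-confirmed influenza, so COVID-19 presenting as influenza-like illness belongs in it.
- *The rate is inflated by a known multiple.* Assuming 30–60% with any follow-up TEAE and 5–10% with influenza-like illness gives 30/10 = 3 to 60/5 = 12, but neither range is in the documents.
- *Test results are ready to tabulate.* The protocol requires testing, but SAP Table 7 names no influenza test. The serology listing shell shows SARS-CoV-2 and HIV columns only.

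**Conclusion.** The point holds as an error in the footnote. As written, the rule for Tables 14.3.1.13 and 14.3.1.14 admits every TEAE collected in follow-up and contradicts SAP Table 6 and the table title. If followed, it makes the at-least-one-TEAE and SOC rows too high or, at best, equal to the intended counts, under a label that does not describe them. The size of the excess cannot be derived from the documents. The per-subject steps of 8.3 to 12.5 percentage points show only that a few extra subjects would change these rows visibly.

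This rests on the footnote being applied as the selection rule and on no case definition existing outside the protocol, SAP and shells. The case report form was not available, so a flag there cannot be excluded. No primary or secondary endpoint is affected.

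**What to change.** Replace the footnote in both tables with a two-part rule: TEAEs reported by the investigator as influenza-like illness (or matching a preferred-term list fixed before unblinding), with onset during the outpatient follow-up period. State when that period starts and ends, including where the first-dose period stops for subjects who receive a second dose. Say whether the flu-season limit in the objective applies. Align SAP Table 6, which refers to reporting and not onset.

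The cost is one footnote, a matching line in Table 6 and, if that route is chosen, a short term list. No new data are needed if the list is used. The investigator-report route requires confirming that such a field exists. A split by influenza and COVID-19 test result is optional, and should be added only once it is confirmed that those results are held in the database.
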